### **1.5. Risk category**

A (HRO art. 7). This project complies with the definition provided: „Ein Forschungsprojekt entspricht der Kategorie A, wenn die vorgesehenen Massnahmen zur Entnahme von biologischem Material oder zur Erhebung von Personendaten nur mit minimalen Risiken und Belastungen verbunden sind.“ The overall risk for participants is minimal, with the risk of harm due to the procedure itself being minimized by the design of the protocol.

All the methods and techniques that are used for data collection are non-invasive and hold minimal risks for participants. The strength exercises as part of the intervention study are identical with the exercises that are being performed in usual fitness and rehabilitation routines. Measurement methods include anthropometric measurements, 3D body surface scanning, ultrasound, isokinetic tests, optical motion capture, IMU measurements via the watchOS and a health- & training-related questionnaire; as well as MRI of the lower limbs in a sub-group of participants.

3D body surface data will be obtained using a structured light body surface scanner at the ZHAW, taking only a few seconds with extremely high accuracy between the scanned and the actual body volume without requiring any physical contact [37]. Anthropometric data will be acquired according to general athlete sports practice in line with recommended standards of the International Society for the Advancement of Kinanthropometry (ISAK). Ultrasound and isokinetic strength tests will be done according to established protocols at the Swiss Olympic Medical Centre but executed at the ZHAW. IMU measurements and optical motion capture require small reflective markers or sensors to be attached to the body surface. Possible skin irritations are very rare and can be locally treated (creams). MRI is the gold standard technique for musculoskeletal imaging without exposing the subject to harmful radiation [38]. In case a person feels uncomfortable inside the MRI tunnel due to claustrophobia or other reasons, the imaging can be discontinued anytime. The same holds for isokinetic tests, ultrasound, 3D body surface scanning and marker-based optical motion capture, should a participant feel uncomfortable or exhausted.

The study design and image parameters are all defined according to previous research by [name] and his research team at the ETH Zurich, the SFISM and the ZHAW [15, 16, 18, 22, 31, 33, 38-43]. Thereby, the Swiss Olympic Medical Center employs a specialised and praxis-oriented team of clinical experts in sports physiotherapy and functional testing of muscular strength and core competencies with state-of-the-art imaging of the musculoskeletal system.

Dynamic COVID-19 guidelines and strict safety and hygiene measures are in place at the ZHAW to ensure minimum risks for participants with regards to the ongoing pandemic.

## 2 PROJECT OBJECTIVES AND DESIGN

### 2.1 Hypothesis and primary objective

Hypothesis: It is hypothesized that advanced subject-specific musculoskeletal modelling in combination with mobile monitoring technology as embedded in the iPhone and Apple Watch allow for accurate prediction of changes in muscle strength and muscle size in the lower limbs following an 8-week strength training intervention of key muscle-tendon groups associated with knee joint stability.

Primary Objective: Prediction of changes in muscle strength in the lower limbs due to different strength training volumes by means of the advanced computational modelling, biomechanical analysis and mobile monitoring technology. Of particular interest is the prediction of 1RM and the prediction of the ratio between hamstrings and quadriceps strength (H:Q ratio) compared against isokinetic strength tests as gold standard. Research has clearly shown that the quantification of 1RM is fundamentally important when it comes to the design of safe and efficient resistance training programs. Improved accuracy in the 1RM prediction compared to preliminary studies (i.e. mean %error of 0.27% in 60% and 7.81% in 80% 1RM assessment [29-34]) is expected through the consideration of data from optical motion capture as well as the additional consideration of subject-specific musculoskeletal anatomy from computational modelling.

Secondary Objective: Assessment of changes in muscle size in the lower limbs due to different strength training volumes using the HMF technique. Of particular interest is the prediction of muscle volume using the HMF technique compared against data from MRI as gold standard, as well as the prediction of adaptation in hamstrings and quadriceps CSA due to the strength training intervention using HMF versus data from ultrasound, respectively. Improved accuracies in the assessment of muscle size compared to preliminary studies (i.e. more than 70% accuracy in muscle volume [22]) are expected through the additional data from anthropometric measurements and the matching of generic model to the study-specific population group including gender.

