mesh. The HMF technique was initially introduced to develop high-order finite element models of individual organs, and later applied and validated for predicting the deformation of muscle-tendon structures in the lower limbs during walking [20].

In the scope of a validation study using data from Magnetic Resonance Imaging (MRI) as gold standard, a generic anatomically-based model was fitted to subject-specific data of six children with cerebral palsy and five children without cerebral palsy. The HMF led to better predictions of muscle volumes and lengths than conventional scaling, with the average error between MRI and HMF being less than 10% for muscle lengths and less than 30% for muscle volume [22]. Further improvements are expected by considering individual body composition (i.e. somatotype) and developing a library of musculoskeletal models for different body shapes and population groups.

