The validity, reliability and accuracy of the *iOS Strength Control app* was assessed outside the laboratory setting in 30 physically healthy subjects, all participating in their own weight training program 1-4 days per week, and for three barbell exercises (i.e. deadlift, bench press, back squat) [33]. Excellent accuracy was demonstrated in exercise recognition and repetition count; yet further development and validation are required to improve the accuracy and reliability in the assessment of exercise execution (joint motion and velocity) and 1RM. Here, previous research has shown that the accuracy in the calculation of 1RM depends on the velocity and joint range of motion during exercise execution, which require more advanced numerical algorithms in biomechanics to be derived.

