HMF 16.5 (2.58) cm^3/kg, p-value > 0.05), respectively [22]. It is expected that the accuracy in the predicted muscle volume is improved in the present study by fitting a generic musculoskeletal model to subjects of similar age and gender, and without significant musculoskeletal impairments, as well as additionally considering subject-specific somatotype based on anthropometric measurements. ANOVA will be performed to analyse the pairwise differences in muscle volumes between the HMF and MRI-based results; and to analyse the pairwise differences in the predicted adaptation of hamstrings and quadriceps CSA between HMF and data from ultrasound before and after strength training intervention, respectively. The data from female and male participants will be analysed combined, as well as independently as two different groups.

The level of significance will be set at  $p < 0.05$  for all statistical tests.

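### Expected accuracy gains rest on historical figures alone, and no previous-versus-new method contrast is planned; for HMF a paired refit in the 12 MRI participants would supply one

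*Combined protocol and SAP*

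**What the plan says.** Section 2.1 attaches an expected gain to each objective.

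- For 1RM, the plan states "Improved accuracy in the 1RM prediction compared to preliminary studies (i.e. mean %error of 0.27% in 60% and 7.81% in 80% 1RM assessment". The gain "is expected through the consideration of data from optical motion capture as well as the additional consideration of subject-specific musculoskeletal anatomy from computational modelling".
- For muscle size, the text reads "Improved accuracies in the assessment of muscle size compared to preliminary studies (i.e. more than 70% accuracy in muscle volume". The gain is put down to anthropometric data and a generic model matched to the study population.

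Section 4.1 repeats the HMF expectation: "It is expected that the accuracy in the predicted muscle volume is improved in the present study by fitting a generic musculoskeletal model". There it is tied to similar age and gender, absence of musculoskeletal impairment, and somatotype.

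The sources of the benchmarks are described in the background. Section 1.2 says that the HMF validation used "six children with cerebral palsy and five children without cerebral palsy". Section 1.3 describes a validation of the app in 30 healthy people on "three barbell exercises (i.e. deadlift, bench press, back squat").

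The analyses in Section 4.1 are predicted against reference: 1RM and H:Q ratio against motion capture and isokinetic tests, HMF volume against MRI, and HMF change in CSA against ultrasound.

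**The concern.** Saying that a method has improved, and that a named addition caused it, needs the method with and without that addition under otherwise equal conditions. Here the method without the addition exists only as a published figure from other people. A difference from that figure mixes the change of method with the change of population and, for 1RM, possibly with differences in exercise, load and error definition that cannot be checked from the documents.

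At stake is how the result is read. Section 2.3 calls the project confirmatory, and the objectives present the gain as the reason for adding motion capture, anatomy, somatotype and a matched model. If HMF does better in healthy adults than it did in children, the report could credit the added inputs when the easier population alone might explain the result. The plan as written has no analysis that would tell the two apart.

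**Working it through.** **1. The plan's own figures.**

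- *HMF benchmark.* Section 1.2 gives an average volume error below 30%, and 100% − 30% = 70%, which matches "more than 70% accuracy in muscle volume". The benchmark is therefore a bound, not an estimate. A new error of, say, 25% might or might not be better than the old one.
- *Sample size (Section 3.1).* d = (200.8 − 170.6) / √((21.4² + 19.0²)/2) = 30.2 / 20.24 = 1.49, taken as 1.5. An exact two-sample t-test at one-sided 0.025 and power 0.9 gives 10.40, rounded up to the stated 11 per group. This concerns change in strength. No figure in the plan sizes prediction error.

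**2. HMF: what changes between benchmark and present study.**

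| | Benchmark (Section 1.2) | Present study (Sections 3.1, 3.3) |
|---|---|---|
| Population | 11 children, 6 with cerebral palsy | 12 healthy adults, 18 to 40 years |
| Fit | previous objective function | skin-layer thickness added |
| Generic model | previous model | matched on age group and gender |
| Reference | MRI | MRI |

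Three things move together. Sections 3.1 and 4.1 themselves name the absence of impairment as a reason to expect a better fit, so population is an acknowledged cause separate from the added inputs.

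**3. 1RM: what the benchmark can mean.** No SD, lift or error definition is given. The meaning of 0.27% depends on the definition (normal errors assumed):

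- If it is a signed mean m with SD s, the mean absolute error is s√(2/π)·exp(−m²/2s²) + m(1 − 2Φ(−m/s)). With m = 0.27 and assumed s = 2, 5 or 10%, this is 1.6, 4.0 or 8.0%.
- If it is a mean absolute error with no bias, s = 0.27 / 0.798 = 0.34%.

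The same number thus fits very different individual accuracy. The 7.81% figure leaves clear numerical room for improvement but has the same gaps.

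**4. What a paired HMF contrast could show.** Old and new fits are scored on the same 12 people against the same MRI (paired t-test, two-sided 0.05).

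- Detectable difference: 1.03 SD of the paired differences at 90% power, 0.89 at 80%.
- 95% CI half-width: 2.201 / √12 = 0.64 SD of the paired differences. With an assumed SD of 5, 10 or 15 percentage points, that is 3.2, 6.4 or 9.5 points.
- In units of the error SD, multiply 1.03 by √(2(1 − ρ)), where ρ is the assumed correlation of old and new errors: 1.46 at ρ = 0, 1.03 at 0.5, 0.80 at 0.7, 0.46 at 0.9.
- For comparison, 11 children against 12 adults, if individual data were available, would detect 1.42 error SDs at 90% power and would still be confounded by population.

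Pairing therefore removes the confounding in every case. It improves precision only as far as the old and new errors are correlated.

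**The case against.** The strongest reply is that no invalid inference is planned. Section 2.1 states an expectation. The hypothesis is accurate prediction, and the endpoints and Section 4.1 assess accuracy against isokinetic tests, motion capture, MRI and ultrasound. The plan also discloses the population difference. All of this stands, and it limits the point to the improvement statements and their attribution.

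Four stronger readings are tempting, and the documents do not support them.

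- *That 0.27% is a signed mean in which errors cancel.* The text says only mean percentage error. The much larger 7.81% makes a signed reading plausible but does not prove it.
- *That the 1RM figures come from different lifts.* The lift behind them is not stated, and the validation in Section 1.3 includes the back squat, while squats are also used here.
- *That the study succeeds or fails by these figures, so that even an unbiased method would usually look worse.* No rule uses them as thresholds. The arithmetic also cuts both ways. With zero bias, an assumed SD of 10% and n = 36, the standard error is 10/6 = 1.67. The observed mean error would fall within 0.27% in 13% of trials, but within 7.81% in practically all (7.81/1.67 = 4.7 standard errors).
- *That Section 4.1 has no within-participant comparison at all.* It has predicted-versus-reference comparisons. What is missing is previous against new.

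It is also fair to say that a full set of paired contrasts for the primary outcomes is not ready. Table 3.3.3 gives no load for the visit exercises and no direct 1RM lift. Motion capture is an added input in Section 2.1 and a measured reference in Section 4.1. No earlier app algorithm for H:Q ratio is described.

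**Conclusion.** The point holds in a limited form. Both improvement statements lean on historical figures, two inputs are added at once for each method, and no planned analysis compares the previous method with the new one. For HMF, a gain over the 70% bound could not be separated from the move from children, more than half with cerebral palsy (6 of 11), to healthy adults. For 1RM, the benchmark cannot be interpreted without its SD, lift and error definition.

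The size of any misattribution cannot be computed, because the documents give no SD of prediction error and no estimate behind the HMF bound. The detectable differences above assume a paired t-test; the SDs and correlations are assumptions shown as ranges. The planned accuracy analyses and the stated sample size are not affected. This is an inexpensive improvement, not a defect that invalidates the study.

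**What to change.** **HMF.** Add to Section 4.1: in the 12 MRI participants, fit the same baseline body-surface data with (a) the previous objective function and generic model and (b) the version with skin-layer thickness and a matched generic model. For hamstrings, quadriceps and triceps surae, compute each participant's absolute percentage volume error against MRI under (a) and (b). Report the paired difference with its 95% CI, and base any statement of HMF improvement on that contrast only. It credits the two changes jointly, not either one alone.

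**1RM.** Keep 0.27% and 7.81% in Section 2.1 as background and draw no improvement claim from them. The phone and watch data are recorded simultaneously with motion capture (Section 3.3), so an app-alone versus app-plus-motion-capture contrast can be added, but only where the test load and a reference independent of motion capture are defined. Do not add a previous-algorithm comparison for H:Q ratio.

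**Cost.** The HMF part needs wording and a re-run of the earlier fit on data already planned, with no extra visits or participants. Precision at n = 12 is low, so the result should be presented as an estimate, and it may not show improvement. The optional 1RM contrast costs more, because its load and reference must be settled first.

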### 2.2 Primary and secondary endpoints

Primary Endpoint: Changes in muscle strength in the lower limbs following the 8-week strength training intervention of the lower limbs in three study groups with different training volumes. The two strength-specific primary outcome parameters are: 1RM and H:Q ratio. Changes in 1RM and H:Q ratio will be derived using the *iOS Strength Control app* and biomechanical analysis before and after the strength training intervention. Primary outcome parameters will be compared between the three study groups in relation to training volumes (Group#1: no training, Group#2: 1 training per week, Group#3: 3 trainings per week). The accuracy in the prediction of 1RM and H:Q ratio will be compared with data from isokinetic strength tests as gold standard.

Secondary Endpoint: Changes in muscle size of the lower limbs following the 8-week strength training intervention of the lower limbs in three study groups with different training volumes. The two secondary outcome parameters are: muscle volume and CSA. Changes in muscle volume and CSA will be derived using the HMF technique in combination with data from 3D body surface scanning and anthropometric measurements before and after the strength training intervention. Secondary outcome parameters will be compared between the three study groups in relation to training volumes (Group#1: no training, Group#2: 1 training per week, Group#3: 3 trainings per week). The accuracy in the derivation of muscle volume and CSA using the HMF technique will be assessed using data from MRI and ultrasound as gold standard.

Key baseline factors that will likely influence the primary and secondary endpoints are strength training experience and gender. The sample size and population group are specified to allow the analysis of gender-specific differences on study results. Thereby, the inclusion/exclusion criteria and study protocol, including a training-related questionnaire, are defined to minimize the bias of training experience.

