The MRI-based assessment of muscle volume for validation of the HMF technique is analyzed independently from the strength training intervention. Thereby, the accuracy of the HMF technique is dependent on the initial generic musculoskeletal model that is used for model fitting, as well as the available subject-specific skin surface and anthropometric data. The level of significance in the difference of muscle volume between HMF and MRI is expected to vary across muscle-tendon groups, as well as between population groups and gender. In particular, no significant differences were found in the predicted volume of semitendinosus and semimembranosus as part of the hamstrings between HMF and MRI in 5 children without CP (MRI 5.1 (0.91) versus HMF 5.0 (0.30)  $\text{cm}^3/\text{kg}$ ,  $p\text{-value} > 0.05$ ) and in the predicted volume of the quadriceps, including vastus lateralis, medialis, intermedius and rectus femoris, in 6 children with CP (MRI 15.9 (3.20) versus HMF 16.5 (2.58)  $\text{cm}^3/\text{kg}$ ,  $p\text{-value} > 0.05$ ), respectively [22]. Based on previous research, it can be expected that additional consideration of somatotype from anthropometric measurements will help to improve model fit by allowing to adjust the relative thickness of the skin layer, and thus segmental inertia properties, via the HMF objective function for individual subjects. Furthermore, it is very likely that the accuracy in fitting results will be improved when fitting a generic musculoskeletal model to subjects of similar age and gender, and without significant musculoskeletal impairments, which will be the case in the present study. Further details to the MRI-based analysis are provided in Subsection 3.3.

All participants have to confirm their voluntary participation with a written informed consent before being submitted to any study procedure.

Inclusion criteria (all participants,  $n=36$ ):

- Healthy participants; and
- Age 18-40 years old; and
- No acute or chronic musculoskeletal symptoms or pain; and
- Experience with strength training (at least 1-year strength training experience with one training session per week or more); and
- Familiar with strength exercises of key muscles associated with knee joint stability.

Exclusion criteria (all participants,  $n=36$ ):

- Acute or chronic musculoskeletal pain; and/or
- Musculoskeletal surgery within the last 12 months; and/or
- Ongoing rehabilitation or treatment of musculoskeletal complaints or injury; and/or

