**Table 3.3.1.** Overall project plan, starting in first quarter of year 1 (May 2021)

	YEAR 1				YEAR 2				YEAR 3				YEAR 4			
Technology set-up and preparation																
Recruitment																
Data acquisition																
Data analysis																
Project management & reporting																

**Table 3.3.2.** Schedule of assessments

Time (weeks)	>-1 day	0	0-2	0-2	8-10
Goal	Info	Screening	Baseline	MRI	Post-intervention
Oral and written information	+				
Check inclusion-/exclusion criteria		+	+		+
Written consent		+			
Participant characteristics		+			
Health- & training-related questionnaire		+			
Anthropometric measurements ISAK			+		+
3D body surface scan			+		+
Ultrasound measurements			+		+
Isokinetic strength tests			+		+
iPhone/watchOS			+		+
Optical motion capture			+		+
MRI				+	(n=12)

**Table 3.3.3.** Summary table listing all project visits, duration, measurements, procedures and instructions to the participants.

TIME	MEASUREMENT	PROCEDURE/EXERCISE	INSTRUCTIONS
1 st Visit: Screening & informed consent (n=36)			

1 h	Informed consent Health- and training-related questionnaire	Inform about study protocol in detail, answer questions, check inclusion and exclusion criteria, assign participant ID, fill in health- and training-related questionnaire.	Participant to carefully read through informed consent and take time for questions and consideration to participate in this study. Participant to fill out consent form and questionnaire.
2nd Visit and 3rd Visit: Baseline measurements & post-intervention measurements (n=36)			
4h	Welcome	Outline procedure and double-check inclusion/exclusion criteria. Withdraw participant if health situation has changed.	Participant self-declares inclusion/exclusion criteria.
	Anthropometric data	Anthropometric measurements according to ISAK standards. 3D body surface scan in relaxed neutral position and image capture from frontal and lateral. Ultrasound of hamstrings and quadriceps according to established protocols at the Swiss Olympic Medical Centre	Participants to stand upright on marked location in relaxed neutral position. 3D body surface scan takes 5-10minutes. The participant is asked to stay as still as possible. Participants to sit upright with their lower limbs relaxed and supported in extended position.

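### The three groups are compared on muscle size derived by HMF, the method under test; no group comparison is planned on ultrasound CSA, although it is measured before and after training in all 36 participants

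*Combined protocol and SAP*

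**What the plan says.** **Outcome and comparison.** Section 2.2 names muscle volume and CSA as the secondary outcome parameters. It states that "Changes in muscle volume and CSA will be derived using the HMF technique", together with body-scan and anthropometric data, and that "Secondary outcome parameters will be compared between the three study groups in relation to training volumes".

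**Status of HMF.** The same section says that HMF accuracy "will be assessed using data from MRI and ultrasound as gold standard". Section 1.2 gives the average error from an earlier validation in 11 children (six with cerebral palsy, five without) as "less than 10% for muscle lengths and less than 30% for muscle volume". Section 2.1 restates the volume figure as "more than 70% accuracy in muscle volume" and expects improvement in this trial.

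**Ultrasound.** Table 3.3.3 lists "Ultrasound of hamstrings and quadriceps according to established protocols at the Swiss Olympic Medical Centre" at Visits 2 and 3, for n=36. Section 3.3 repeats the baseline measurements at Visit 3 under the same protocols. Sections 2.1, 2.3, 3.3 and 4.1 use the ultrasound values only for comparison with HMF.

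**Analysis.** Section 4.1 plans ANOVA of pairwise differences between HMF and MRI volumes and between HMF and ultrasound CSA adaptation. It specifies no between-group test of muscle size by either method.

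**MRI.** Sections 2.3 and 3.1 give one scan, at baseline, in 12 participants.

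**The concern.** The secondary endpoint does two jobs. It estimates the effect of training volume on muscle size, and it shows whether HMF can detect that effect. As planned, both rest on HMF output. HMF does not observe muscle: Section 1.2 explains that embedded muscle is derived from deformation of a generic model's skin mesh. A fit that stays too close to the generic model would understate differences between people, and might understate change within a person.

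If the HMF values then show no group difference, there are two explanations: training volume made little difference, or HMF did not register the difference it made. For hamstrings and quadriceps CSA, the data that would help separate these are already scheduled, but no group comparison on them is planned.

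**Working it through.** **1. The plan's own error figure.** An average volume error below 30% (Section 1.2) and accuracy above 70% (Section 2.1) agree: 100 − 30 = 70. The figure bounds an average, for cross-sectional volume, in children. The documents give no HMF error for CSA or for change. The only sample-size calculation (Section 3.1, 11 per group) concerns 1RM, so there is no power figure for muscle size to reproduce.

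**2. What is measured before and after training.**

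| Quantity | HMF | Reference method |
|---|---|---|
| Hamstrings and quadriceps CSA, change | Visits 2 and 3 | Ultrasound, Visits 2 and 3, n=36 |
| Muscle volume, change | Visits 2 and 3 | None (MRI at baseline only, n=12) |
| Triceps surae size, change | Visits 2 and 3 | None |

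A measured group comparison is therefore possible for the first row only.

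**3. Spread of HMF against MRI.** The inputs are in Sections 3.1 and 4.1, as mean (SD) in cm³/kg.

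- Semitendinosus and semimembranosus, 5 children without cerebral palsy: "MRI 5.1 (0.91) versus HMF 5.0 (0.30" in brackets for HMF. SD ratio 0.30/0.91 = 0.33.
- Quadriceps, 6 children with cerebral palsy: SD 3.20 by MRI and 2.58 by HMF. SD ratio 2.58/3.20 = 0.81.

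The regression slope of HMF on MRI is r × SD(HMF)/SD(MRI). In these samples it cannot exceed 0.33 and 0.81, the values reached at r = 1.

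**4. Precision of those ratios.** Treat the two SDs as independent, with F = (SD(MRI)/SD(HMF))² and limits equal to ratio ÷ √F(0.975) and ratio × √F(0.975).

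- Hamstring part: F = (0.91/0.30)² = 9.20 on 4 and 4 df, two-sided p = 0.054. With F(0.975) = 9.60, √9.60 = 3.10, the 95% interval is 0.11 to 1.02.
- Quadriceps: F = (3.20/2.58)² = 1.54 on 5 and 5 df, p = 0.65. With F(0.975) = 7.15, √7.15 = 2.67, the interval is 0.30 to 2.16.

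The data are in fact paired. The paired test for the hamstring part gives p from about 0.10 at r = 0 to 0.005 at r = 0.95, and the documents do not give r. Compression is suggested for the hamstring part and not demonstrable for quadriceps.

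**5. What would decide whether HMF change is usable.** This step is an illustration in which every input is assumed: true group difference in change 5%, SD of true change 5/1.5 = 3.33%, 12 per group, two-sided 0.05. Let e be the HMF error SD per visit and ρ the correlation of a person's errors across visits. Then SD of error in change = e√(2(1 − ρ)) and d = 5/√(3.33² + SD²). Without error, d = 1.5 and power is 94%.

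| e | ρ = 0 | ρ = 0.9 | ρ = 0.99 |
|---|---|---|---|
| 10% | 13% | 56% | 90% |
| 30% | 6% | 14% | 58% |

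For example, with e = 10% and ρ = 0.9, SD = 10 × √0.2 = 4.47, d = 5/√(11.1 + 20.0) = 0.90 and power is 56%. The answer turns on how far the error repeats within a person, and the documents give no figure for that.

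**The case against.** **HMF is the stated objective.** Section 2.1 sets out to assess change in muscle size with HMF, so a group comparison on HMF values is deliberate. This stands. It is a reason to add ultrasound beside HMF and not to replace HMF.

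**The agreement analysis already covers the risk.** Section 4.1 compares HMF and ultrasound adaptation, which gives some evidence on whether HMF misses change in CSA. A claim that a null result could never be interpreted would therefore go too far. But the help is partial: a non-significant pairwise difference does not show that HMF tracks change, and the analysis does not estimate the training effect on measured CSA.

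**Stable error cancels in a change score.** This is true of a constant additive error within a person. It is not true of a slope below 1.

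**The method has been improved.** Adult, gender-matched generic models and somatotype data may raise accuracy. That is an expectation which the trial is meant to test.

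**Stronger readings that the documents do not support.** A reader might infer that HMF is wrong by as much as 30% in this trial; the figure is an average, for volume, in children. A reader might also infer that training gains will appear at a third of their true size in hamstrings. That would carry a between-child slope for volume, from 5 children and two muscles, over to within-adult change in CSA, and nothing in the documents supports the step.

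**Conclusion.** The concern holds as an omission: the plan prespecifies no group comparison on the reference measurement it already collects for hamstrings and quadriceps CSA. This rests on the text alone. The size of any loss cannot be fixed from the documents. The SD ratios of 0.33 and 0.81 suggest compression but have intervals of about 0.11 to 1.02 and 0.30 to 2.16, and they describe differences between children, not change in adults. The difficulty in interpreting a null result depends on the assumption that HMF under-tracks change. The point concerns a secondary endpoint. It should be changed, because the remedy is nearly free, but it does not threaten the primary objective.

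**What to change.** - **Section 2.2:** add change in hamstrings and quadriceps CSA measured by ultrasound, compared between the three groups, as the measured estimate of the training effect. Keep the HMF-derived comparison beside it as the method under test, so that the objective in Section 2.1 is unchanged.
- **Section 4.1:** specify the three-group test for ultrasound CSA change and the parallel test for HMF CSA change, with group differences and 95% intervals. Report the slope of HMF change on ultrasound change, with its interval, in addition to the pairwise ANOVA.
- **Both sections:** label group comparisons of volume change and of triceps surae as exploratory, because they have no measured before-and-after value.

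The cost is one extra secondary analysis and small wording changes. Participants, visits and measurements stay as planned.

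The fix does not make HMF volume change verifiable in this trial; that remains a limitation to state.
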